7.1.2 Unsolicited Adverse Events

An unsolicited adverse event is an adverse event that was not solicited using a Subject Diary and that was spontaneously communicated by a subject who has signed the informed consent.

Potential unsolicited AEs may be medically attended (defined as symptoms or illnesses requiring hospitalization, or emergency room visit, or visit to/by a health care provider), or were of concern to the subject. In case of such events, subjects will be instructed to contact the site as soon as possible to report the event(s). The detailed information about the reported unsolicited AEs will be collected by the qualified site personnel during the interview and will be documented in the subject’s records.

Unsolicited AEs that are not medically attended nor perceived as a concern by subjects will be collected during interview with the subject and by review of available medical records at the next visit (see [section 5.3, Post-vaccination Visit\(s\)](#)).

7.1.3 Evaluation of Adverse Events

Every effort should be made by the investigator to evaluate safety information reported by a subject for an underlying diagnosis and to capture this diagnosis as the event in the AE page. In other words, the practice of reporting only symptoms (e.g., “cough” or “ear pain”)

are better reported according to the underlying cause (e.g., “asthma exacerbation” or “otitis media”).

The severity of events reported on the Adverse Events CRF will be determined by the investigator as:

Mild: transient with no limitation in normal daily activity.

Moderate: some limitation in normal daily activity. Severe:
unable to perform normal daily activity.

The relationship of the study treatment to an AE will be determined by the investigator based on the following definitions:

1. Not Related

The AE is not related to an investigational vaccine if there is evidence that clearly indicates an alternative explanation. If the subject has not received the vaccine, the timing of the exposure to the vaccine and the onset of the AE are not reasonably related in time, or other facts, evidence or arguments exist that reasonably suggest an alternative explanation, then the AE is not related.

2. Possibly Related

The administration of the investigational vaccine and AE are considered reasonably related in time and the AE could be explained by exposure to the investigational vaccine or by other causes. 3. Probably Related

Exposure to the investigational vaccine and AE are reasonably related in time and no alternative explanation has been identified.

The relationship of the study treatment to an unsolicited AE will be determined by the investigator.

Note: solicited AEs will not be evaluated for relationship to study treatment. Grading for severity of solicited local and systemic AEs is described in [section 7.1.1, Solicited Adverse Events](#).

Adverse events will also be evaluated by the investigator for the co-existence of any of the other following conditions:

- “Medically attended adverse event”: an adverse event that leads to a visit to a healthcare provider.
- “New onset of chronic disease” (NOCD): an adverse event that represents a new diagnosis of a chronic medical condition that was not present or suspected in a subject prior to study enrolment.

- AEs leading to withdrawal: adverse events leading to study or vaccine withdrawal.
- Potential immune-mediated diseases (pIMDs): a subset of AEs that include autoimmune diseases and other inflammatory and/or neurologic disorders of interest which may or may not have an autoimmune aetiology. In this study, only the pIMDs reported in the table below will be collected. However if other pIMDs are discovered during development of the vaccine, the table will be revised and updated accordingly.

Musculoskeletal disorders	Spondyloarthritis, including ankylosing spondylitis, reactive arthritis (Reiter's Syndrome) and undifferentiated spondyloarthritis
Blood disorders	Autoimmune neutropenia

If solicited or unsolicited adverse events have been reported and the subject indicated that the symptoms required medical attendance or were of concern, the subject must be contacted for further information.

When the subject is contacted for any of these reasons, the contact must be documented in the subject's source documentation.

All AEs, regardless of severity, will be monitored until resolution or until the investigator assesses them as chronic or stable. All subjects experiencing AEs - whether considered associated with the use of the study vaccine or not - must be monitored until symptoms subside and any abnormal laboratory values have returned to baseline, or until there is a satisfactory explanation for the changes observed, or until death, in which case a full pathologist's report should be supplied, if possible. The investigator's assessment of ongoing Adverse Events at the time of each subject's last visit should be documented in the subject's medical chart.

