		Grade 1 Mild	Grade 2 Moderate	Grade 3 Severe
Injection site Erythema (Captured as measurements in millimeters)	1-24 mm	25-50 mm	51-100 mm	> 100 mm

Injection site Induration (Captured as measurements in millimeters)	1-24 mm	25-50 mm	51-100 mm	> 100 mm
Injection site Pain	No pain	Present but does not interfere with activity	Interferes with activity	Prevents daily activity

Solicited Systemic Adverse Events

These include headache, arthralgia, chills, fatigue, malaise, myalgia, and fever (body temperature measured orally). They will be assessed using the scoring system reported in a table below.

Table 7 Grading of solicited systemic adverse events

Solicited systemic adverse events	Grade 0 Absent	Present - Grading of Severity*		
		Grade 1 Mild	Grade 2 Moderate	Grade 3 Severe
Headache	No headache	Present but does not interfere with activity	Interferes with activity	Prevents daily activity
Arthralgia	No arthralgia	Present but does not interfere with activity	Interferes with activity	Prevents daily activity
Chills	No chills	Present but does not interfere with activity	Interferes with activity	Prevents daily activity
Fatigue	No fatigue	No interference with activity	Some interference	Significant; prevents daily
			with activity	activity
Malaise	No malaise	No interference with activity	Some interference with activity	Significant; prevents daily activity
Myalgia	No myalgia	Present but does not interfere with activity	Interferes with activity	Prevents daily activity
Fever as a Body temperature (Captured as measurements in degrees Celsius)	≤ 37.9 °C	≥ 38.0 – 38.9°C	≥ 39.0 – 39.9°C	≥ 40.0°C
	Oral Temperature: <35.5 °C to ≥38.0 °C			

Other Solicited Adverse Events

These include use of analgesics/antipyretics. It will be assessed using the scoring system reported in a table below.

Other Solicited adverse events	Grade 0 Absent	Present - Grading of Severity			
		Grade 1 Mild	Grade 2 Moderate	Grade 3 Severe	
Use of analgesics/ antipyretics		Categorized as “yes” or “no”			

The study staff must review the data entered into the Subject Diary as described in [section 3.4.2, Tools Used for Data Collection](#) and [section 5.3.1, Follow-up Clinic Visit\(s\)](#).

Note: Any solicited adverse event that meets any of the following criteria must be entered into subjects’ source document (see [section 9.1, Source Documentation](#)) and also as an adverse event on the Adverse Event CRF:

- Solicited local or systemic adverse event that continues beyond day 7 after vaccination.

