8.4.2.1.3 Analysis of Unsolicited Adverse Events

This analysis applies to all adverse events occurring during the study, judged either as probably related, possibly related, or not related to vaccination by the investigator, recorded in AE CRF, with a start date on or after the date of vaccination. AE starting prior to the vaccination will only be listed. The original verbatim terms used by investigators to identify adverse events in the CRFs will be mapped to preferred terms using the MedDRA dictionary. The adverse events will then be grouped by MedDRA preferred terms into frequency tables according to system organ class.

All reported adverse events, as well as adverse events judged by the investigator as at least possibly related to study vaccine, will be summarized according to system organ class and preferred term within system organ class. These summaries will be presented by vaccination group and by interval of study observation. When an adverse event occurs more than once for a subject, the maximal severity and strongest relationship to the vaccine group will be counted.

Separate summaries will be produced for the following categories:

- Serious adverse events
- Adverse events that are possibly or probably related to vaccine

- Adverse events of special interest
- New onset of chronic disease
- Potential immune-mediated diseases (pIMDs) adverse event leading to withdrawal • Adverse events leading to a medically attended visit
- Adverse event by data source.

Data listings of all adverse events will be provided by subject. In addition, adverse events in the categories above will be provided as listed data.

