6.5.2.3. Unsolicited Adverse Events

All the unsolicited adverse events occurring during the study, judged either as probably related, possibly related, or not related to vaccination by the investigator, will be recorded. The original verbatim terms used by investigators to identify adverse events in the CRFs will be mapped to preferred terms using the MedDRA dictionary. The unsolicited adverse events will then be grouped by MedDRA preferred terms into frequency tables according to system organ class. Adverse events judged by the investigator as at least possibly related to study vaccine will be summarized by vaccine group, according to system organ class and preferred term within system organ class. When an unsolicited adverse event occurs more than once for a subject, the maximal severity and strongest relationship to the vaccine group will be counted.

Only vaccine-emergent adverse events (see **section 7.1** of protocol for definition) will be analyzed, i.e., excluding those after a subject has given informed consent but before vaccination.

The summaries will be presented for all study period and will include frequency distributions of the different adverse events:

- Onset between day 1 and study termination (all study period).

The analysis of unsolicited adverse events comprises the following categories:

- Any unsolicited adverse event.
- Possibly or probably related unsolicited adverse events.
- Unsolicited adverse events leading to death.
- Serious adverse events.
- Possibly or probably related serious adverse event.
- Unsolicited adverse events leading to premature withdrawal from study.
- Unsolicited adverse events leading to hospitalization.
- Unsolicited adverse events of special interest.

- Solicited adverse events continuing beyond day 7 will be coded by MedDRA and combined with the respective unsolicited adverse events.

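### Protocol 7.1.3 conflicts with 7.1.1, 8.4.2.1.3 and SAP 6.5.2.3 on whether a solicited reaction lasting beyond Day 7 gets the causality judgement that the related-AE table needs

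*Protocol*

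**What the plan says.** The references are to Protocol Version 2 and the final SAP.

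- **Protocol 7.1.1** lists the solicited events that must go into the source document "and also as an adverse event on the Adverse Event CRF". The first criterion is: "Solicited local or systemic adverse event that continues beyond day 7 after vaccination".
- **Protocol 7.1.3** opens its causality text with a general rule: "The relationship of the study treatment to an AE will be determined by the investigator based on the following definitions". After the definitions it adds a rule for one class: "The relationship of the study treatment to an unsolicited AE will be determined by the investigator". It then makes an exclusion for the other class: "Note: solicited AEs will not be evaluated for relationship to study treatment". No exception is given for solicited events moved to the AE CRF.
- **Protocol 8.4.2.1.3** describes the events in the unsolicited analysis as "judged either as probably related, possibly related, or not related to vaccination by the investigator, recorded in AE CRF".
- **SAP 6.5.2.3** states: "Solicited adverse events continuing beyond day 7 will be coded by MedDRA and combined with the respective unsolicited adverse events". The same section has a category for any unsolicited event and another for those the investigator judged possibly or probably related.

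Neither document says whether a prolonged solicited event on the AE CRF receives a relationship entry, or how an event without one is shown.

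**The concern.** A solicited reaction lasting beyond Day 7 meets two rules that point in opposite directions. As a solicited event it is not to be assessed for causality. As an AE CRF entry, pooled with the unsolicited events, it sits in an analysis that presumes a causality judgement. Site staff following the note would record none, and the related-AE summary would then be incomplete. Staff who treat it like any other AE CRF entry would record one. What the table contains would depend on site habit and not on the plan.

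This matters because local and systemic reactions that begin after vaccination and persist are events for which a link to the vaccine is especially plausible. The trial is descriptive and its safety output consists of tables of this kind, in groups small enough for one subject to be visible.

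**Working it through.** The documents state no figure on this point, so the check is mainly a comparison of text.

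**1. Does a prolonged diary reaction stop being solicited?** No section says so. Protocol 7.1.1 changes where the event is recorded and does not rename it. Protocol 7.1.2 defines an unsolicited event as one that was not solicited through the Subject Diary, which a diary-recorded reaction does not meet. Where the protocol wants reclassification it says so: under 3.4.2, newly described safety information, including a solicited event, is to be reported as unsolicited. Protocol 7.1.1 has no equivalent wording.

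**2. Does the exclusion in 7.1.3 then apply?** On its wording, yes. It is unqualified, and it comes after both the general rule and the rule for unsolicited events.

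**3. What does the related table require?** SAP 6.5.2.3 includes events that the investigator judged at least possibly related. An event with no judgement does not meet that condition, whatever default might be assumed for missing values. The SAP offers no such default; its derivation rules in 11.2 deal only with incomplete dates.

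**4. Result if the note is followed literally.** The event is merged and counts under any unsolicited event in the SAP table, but cannot enter the related rows. It does not fit Protocol 8.4.2.1.3 either, which describes its events as already judged.

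**5. Which events are outside the gap?** Serious solicited events, because Protocol 7.1.4 has every SAE assessed for relationship. Also verbally reported solicited events, because 3.4.2 makes them unsolicited and 7.1.3 has those assessed. What remains is non-serious, diary-recorded solicited events persisting beyond Day 7.

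**6. Scale.** The planned numbers come from the study design table (Protocol Table 1, SAP Table 2-1) and the safety groups from SAP 6.5.2:

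- Shigella group: 5 + 4 + 2 + 4 + 5 = 20
- Placebo plus naïve: 4 + 26 = 30
- Total: 20 + 30 = 50

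One subject whose only related event would be an unassessed prolonged reaction changes the related percentage by 100 × 1/n:

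- Shigella group: 100 × 1/20 = 5.0 points
- Placebo plus naïve: 100 × 1/30 = 3.3 points
- Total: 100 × 1/50 = 2.0 points

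These are weights per subject and do not predict how many subjects will be affected. Neither document gives a rate of reactions lasting beyond Day 7.

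**The case against.** The best case for the plan is that the note in 7.1.3 was meant for reactions that stay in the diary. The sentence after it points to the severity grading of solicited events in 7.1.1, whereas AE CRF events have their own severity scale in 7.1.3. Protocol 7.1.4 shows that the AE CRF page carries a relationship field. Protocol 8.4.2.1.3 presumes that the events it analyses are judged. On this reading a transferred reaction is assessed like any other entry and nothing is lost. The reading is possible, and it is why the finding is a conflict between sections and not a demonstrated loss of events. It does not remove the conflict, because the note has no such limit.

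It is also fair to say that little is hidden. No secondary safety endpoint uses relatedness. Diary reactions are shown by day and by maximum severity (SAP 6.5.2.2). Prolonged ones also appear among all unsolicited events and in the combined summary of SAP 6.5.2.4, although that summary specifies no breakdown by relationship. All of this stands, and it limits the point to one supporting table.

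A reader might infer that the gap could hide early reactive arthritis, since arthralgia is a solicited symptom. The documents do not support that. Protocol 7.1.3 asks for the underlying diagnosis to be recorded, reactive arthritis is an AESI with its own summary, and 7.1.5 puts every AESI on the AE page whatever its grade. None of these steps depends on a causality value for the preceding arthralgia.

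**Conclusion.** The sections conflict and need to be reconciled. Protocol 7.1.3 excludes solicited events from causality assessment without exception. Protocol 7.1.1 and 8.4.2.1.3, together with SAP 6.5.2.3, bring prolonged ones into an analysis built on that assessment.

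A reader might go further and conclude that every prolonged solicited event drops out of the related counts. That is too strong in two ways. The loss follows only if the note overrides the AE CRF route, which the documents leave open. Serious and verbally reported events are assessed in any case.

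The consequence is limited to the descriptive related-AE summary: 5.0, 3.3 or 2.0 percentage points per affected subject in the Shigella, placebo-plus-naïve and total columns. These values assume full planned enrolment, all subjects in the denominator, and no other related event in the affected subject. With fewer subjects in the denominator the shift per subject is larger. The number of affected subjects is unknown, so no total effect can be given. The change is worth making because it costs little and settles what sites collect.

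**What to change.** **Protocol 7.1.3:** limit the note to solicited events recorded only in the Subject Diary, and require an investigator relationship assessment for every solicited event entered on the AE CRF under 7.1.1.

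**SAP 6.5.2.3:** state that a merged solicited event with no relationship entry is shown in a separate row, labelled as relationship not assessed. It should be neither left out nor imputed as related. Imputation would conflict with a table defined by the investigator's judgement.

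**Cost:** one sentence in each document and one extra table row. Protocol 7.1.4 indicates that the AE CRF page already holds the relationship judgement, so no new form is implied. Sites assess a few more events, and the related-AE percentage may come out somewhat higher than under a literal reading of the note.

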7.1.4 Serious Adverse Events

A serious adverse event (SAE) is defined as any untoward medical occurrence that at any dose results in one or more of the following:

- Death.
- Is life-threatening (i.e., the subject was, in the opinion of the investigator, at immediate risk of death from the event as it occurred); it does not refer to an event which hypothetically might have caused death if it were more severe.
- Required or prolonged hospitalization.
- Persistent or significant disability/incapacity (i.e., the event causes a substantial disruption of a person's ability to conduct normal life functions).
- Congenital anomaly/or birth defect.

- An important and significant medical event that may not be immediately life threatening or resulting in death or hospitalization but, based upon appropriate medical judgment, may jeopardize the subject or may require intervention to prevent one of the other outcomes listed above.

Adverse events which do not fall into these categories are defined as non-serious.

It should be noted that a severe adverse event need not be serious in nature and that a serious adverse event need not, by definition, be severe.

Serious adverse events will be captured both on the Vaccines Serious Adverse Event (VSAE) form as well as on the AE CRF. All SAEs will be evaluated by the investigator for relationship of the event to study vaccine. SAEs that are judged to be possibly or probably related to the study vaccine should be reported to the Sponsor as related events. The relationship of the study treatment to an SAE will be determined by the investigator based on the following definitions:

1. Related

The SAE is judged by the investigator to be possibly or probably related to the study vaccine on the AE CRF page (see [section 7.1.3, Evaluation of Adverse Events](#)).

2. Not Related

The SAE is not related if exposure to the study vaccine has not occurred, **or** the occurrence of the SAE is not reasonably related in time, **or** the SAE is considered unlikely to be related to use of the study vaccine, i.e., there are no facts (evidence) or arguments to suggest a causal relationship.

The relationship of the study vaccine to an SAE will be determined by the investigator.

In addition, SAEs will be evaluated by the Sponsor or designee for “expectedness.” An unexpected AE is one that is not listed in the current Summary of Product Characteristics or the Investigator’s Brochure or an event that is by nature more specific or more severe than a listed event.

In addition, a pre-existing event or condition that results in hospitalization should be recorded on the Medical History CRF. If the onset of an event occurred before the subject entered the study (e.g., any pre-planned hospitalization for conditions like cosmetic treatments or for non-emergency routine visits for a pre-existing condition), the hospitalization would not lead to an AE being classified as serious unless, in the view of the investigator, hospitalization was prolonged as a result of participation in the clinical study or was necessary due to a worsening of the pre-existing condition.

7.1.4.1 Adverse Events of Special Interest

Adverse events of special interest (AESIs) are predefined adverse events that will be specifically highlighted to the investigator and will be summarized separately. Only AESI meeting the definition of SAE will be categorized and reported as such in this study.

Reactive arthritis (ReA) or Neutropenia will be collected and analyzed as an AESI for this study.

Reactive arthritis is defined as non-purulent joint inflammation that develops in response to an infection in another part of the body. Since the inflammation is triggered by a previous condition, it is termed “reactive”. Intestinal pathogens that have been associated with reactive arthritis include *Campylobacter*, *Salmonella*, *Yersinia*, *Clostridium difficile*, and *Shigella*. If reactive arthritis is caused by an auto immune response, there is at least a possibility that it could be initiated by vaccination of susceptible people with the 1790GAAH vaccine.

For diagnosis of ReA, imaging and aspiration are not required (unless clinically indicated).

Neutropenia is defined as decrease of neutrophil count asymptotically or symptomatically with ANC $<1.8 \times 10^9/L$, occurring at 7 days after vaccination. Its graded from grade 1 to 4 basing on neutrophil counts as follows: Grade 1 ANC $1.5- <1.8 \times 10^9/L$, Grade 2 ANC $<1.5 \times 10^9/L$, Grade 3 ANC $1.0- 0.5 \times 10^9/L$, and Grade 4 $<0.5 \times 10^9/L$.

This is completely diagnosed by laboratory testing for complete blood count.

